Sacral nerve stimulation (SNS) is a well-established treatment for refractory urinary urgency, frequency, retention and urge incontinence as well as fecal incontinence. Patients whose symptoms are refractory to more conservative therapies such as behavioral modification and/or medications are candidates for SNS. Prior to placement of the implant, patients must first undergo percutaneous nerve evaluation (PNE) and test stimulation. During this outpatient procedure the patient is placed in the prone position and a needle is inserted into the S3 foramen bilaterally under local anesthetic. Correct placement of the needle is confirmed by eliciting the appropriate nerve stimulation responses, and in some cases by the use of fluoroscopy. When correct position is achieved, a temporary monopolar percutaneous lead is placed through each needle bilaterally and the needles removed. The leads are attached to an external stimulator that is worn for a period of 3 to 7 days. Patients keep voiding diaries during the test stimulation, and if they demonstrate a 50% or greater improvement in symptoms they are eligible for implantation of the permanent timed lead and pacemaker-like stimulator, or IPG. Most studies report a 40% to 50% implantation rate following PNE (1). While some practitioners reserve fluoroscopic guidance solely for placement of the permanent timed lead, some prefer to use fluoroscopy when placing the temporary lead during PNE as well.

Methods and Procedures:

Patients with refractory urinary or fecal urgency, frequency, or incontinence undergoing peripheral nerve evaluation prior to InterStim implantation will be recruited from the HCOC Urogynecology outpatient office and will be consented for participation in the study during their preoperative office visit or on the day of their procedure. We plan to enroll approximately 200 patients in the study. Subject participation will last approximately 3 months.

Patients will be randomized just before PNE by block randomization to either Group 1 or Group 2. .

Group 1: Fluoroscopy guided PNE

Group 2: PNE without fluoroscopic guidance

Patients randomized to Group 1 will have their PNE performed in the HCOC outpatient surgery center or at the Jewish East Medical Center under local anesthetic with fluoroscopic guidance. Fluoroscopy will be used to confirm correct needle and subsequent lead placement.

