Patients randomized to Group 2 will also have the PNE performed in the HCOC outpatient surgery center or at the Jewish East Medical Center under local anesthetic but no fluoroscopy will be used. (This is our current practice for PNEs.)

As is standard practice following PNE, patients will complete a 3-7 day voiding diary pre and post procedure, and if a 50% or greater improvement in symptoms (number of voids, number of incontinent episodes, or less urgency) is documented they will be eligible for implantation of the tined lead and implantable pulse generator (IPG). We will then calculate implantation rates between the two groups.

Inclusion Criteria:

- Women age ≥ 18
- English speakers
- Patients with urinary urgency, frequency, or urge incontinence refractory to at least 1 other intervention who elect to undergo PNE

Exclusion Criteria:

- Patients in whom bilateral leads cannot be placed
- Pregnant women
- Prisoners
- Less than 18 years of age

Data Sources:

- Electronic medical record at HCOC will be used to collect data

Data Collection:

The following information will be collected from the electronic medical record and entered into an encrypted excel spreadsheet:

- Age
- Race
- BMI
- Preoperative diagnosis
- Previous treatments for urinary urgency, frequency, retention, and/or urinary or fecal incontinence
- Percent improvement in symptoms as determined by pre and post PNE voiding diaries
- Whether or not InterStim implanted within 3 months of PNE
- Date of PNE
- Date of implantation of InterStim (if applicable)
- PFDI-20, PISQ-12, PFIQ-7 quality of life surveys

Data Analysis and Statistical Methods:

The primary outcome will be the difference in the rate of implantation of InterStim after PNE in each group. Secondary outcomes will identify demographic and perioperative factors associated with increased rates of implantation. Demographic factors will include age, race, previous treatments, and percent improvement in symptoms as determined by pre and post PNE voiding diaries. Continuous variables will be compared using the non-paired T-test and categorical variables will be compared using the chi-squared test.

Data Handling/Storage

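### Does the secondary analysis of perioperative factors fail because the plan names no such factor and lists almost no procedural data?

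*Combined protocol and SAP*

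**What the plan says.** The primary outcome is the difference between arms in the rate of InterStim implantation after PNE. The secondary outcome is given in one sentence of Data Analysis and Statistical Methods: "Secondary outcomes will identify demographic and perioperative factors associated with increased rates of implantation". The next sentence spells out one of its two classes: "Demographic factors will include age, race, previous treatments, and percent improvement in symptoms as determined by pre and post PNE voiding diaries". No sentence does the same for perioperative factors, and the word does not occur again in the document. The section ends with a t-test for continuous variables and a chi-squared test for categorical ones.

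The Data Collection section opens with "The following information will be collected from the electronic medical record and entered into an encrypted excel spreadsheet" and gives ten items. Data Sources adds: "Electronic medical record at HCOC will be used to collect data". Data Handling/Storage says that paper forms will also be used and entered into the study database, but does not give their fields.

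Several procedural details are described without being listed for collection. There are two possible facilities ("PNE performed in the HCOC outpatient surgery center or at the Jewish East Medical Center"). Needle position is checked by response ("Correct placement of the needle is confirmed by eliciting the appropriate nerve stimulation responses"). Test stimulation lasts 3 to 7 days. Lead migration and other complications appear under Potential Risks.

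**The concern.** An outcome should be computable from the data that the plan says it will collect. Here the demographic half is fully matched and the perioperative half is not matched at all. If the listed items were all that was recorded, there would be nothing procedural to analyse except a date.

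The second worry is selection. Factors that are not named in advance may be chosen after implantation results are known. With only unadjusted tests specified, a reader could not then tell a planned factor from one picked because it showed an association.

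Percent improvement does not obviously rescue the position. The plan labels it demographic. It is also the quantity behind the 50% threshold for implant eligibility, so its association with implantation is largely built in.

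**Working it through.** No formula applies. The check is a count, followed by a reading of the sections against one another.

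**Count of the Data Collection list**

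| Item | Describes how the PNE was done? |
|---|---|
| Age | No |
| Race | No |
| BMI | No |
| Preoperative diagnosis | No (baseline) |
| Previous treatments | No (baseline) |
| Percent improvement by diary | No (response to the test) |
| Implanted within 3 months | No (outcome) |
| Date of PNE | Yes, but only a date |
| Date of implantation | No (outcome) |
| Three quality-of-life surveys, one entry | No |

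That is ten items, one of them procedural. Of the four factors named in the analysis section, all four are on the list. Perioperative factors named: zero. The observation stands.

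**Is the list exhaustive?** The inference from not listed to not collected needs it to be. It is not. Randomised group is absent from the ten items, yet the primary outcome compares the two groups, so allocation must be recorded somewhere. The list is also introduced as what comes from the electronic record. The data-security text treats the medical record and the paper forms as alternative sources of entry. Since the forms' fields are not given, absence from the list does not show that an item goes unrecorded.

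**Can the data be recovered later?** Under Protection of Human Subjects/Security of Data/Conduct of Study, the linking key is destroyed when two conditions both hold: data collection is complete, and nobody needs to go back to a subject's chart. While a perioperative factor is still to be abstracted, the second condition is not met. The key clause therefore sets no deadline that defeats the analysis. The document does not say whether the HCOC record holds procedure notes from the second facility. That affects the effort of abstraction, and it does not show that the data cannot be had.

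**What depends on the undefined term?** The stated hypothesis concerns conversion with and without fluoroscopy. The target of about 200 patients is not tied to the secondary analysis. No error rate, ranking or decision is attached to it.

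**Would specifying factors now correct anything?** Facility, days of stimulation, type of S3 response and lead migration are mentioned as setting, procedure or risk, never as candidate predictors. Choosing among them would be a reviewer's preference. The document speaks only of appropriate responses and gives no categories, so a response-type variable could not be defined from it. Deleting the word instead would alter no result.

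**The case for a change.** The strongest case for acting is that the remedy is nearly free: name a few factors and add a few fields, or strike one word. Without that, nothing tells the staff who abstract charts that procedural details are wanted, and a set of factors chosen late is open to selection. It can fairly be added that the two variables which might fill the gap do not fit well. Use of fluoroscopy is an intraoperative factor known for every patient, but it is already the primary comparison. Percent improvement is plainly not demographic, but the plan calls it so.

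What stands is that this half of the secondary outcome is not prespecified. A careful report should therefore present any perioperative association as exploratory and say how the factors were chosen. It does not stand that the analysis is undeliverable, because neither the list nor the key clause supports that.

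A related point should not add weight here. The exclusion of "Patients in whom bilateral leads cannot be placed" can be established only during the procedure, whereas "Patients will be randomized just before PNE by block randomization to either Group 1 or Group 2". That is a question of exclusion after randomisation and of the primary analysis population. It should be judged separately; recording bilateral placement by arm would describe it without resolving it.

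**Conclusion.** No change is needed. The plan leaves one word undefined in a secondary analysis: zero perioperative factors are named, and one of ten listed items is procedural. This is missing detail of a kind that analysts fill sensibly, by fixing a short set of available factors before looking at implantation results and labelling the findings exploratory. The effect on the primary comparison is nil, and no figure in the plan changes.

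The conclusion rests on two readings. The first is that the secondary analysis is descriptive, which fits the absence of any hypothesis or error rate attached to it. The second is that procedural details can be found in charts or on the paper forms, which the document neither confirms nor rules out. If the second reading failed, the perioperative part would go unreported, and the trial's main question would still be unaffected.

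### Percent diary improvement is to be tested as a factor for implantation, although improvement on those same diaries decides who is eligible, so the result would largely restate the rule

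*Combined protocol and SAP*

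**What the plan says.** The secondary aim is set out under Data Analysis and Statistical Methods: "Secondary outcomes will identify demographic and perioperative factors associated with increased rates of implantation". The next sentence gives the list: "Demographic factors will include age, race, previous treatments, and percent improvement in symptoms as determined by pre and post PNE voiding diaries". Continuous variables go to an unpaired t-test and categorical variables to a chi-squared test. The groups for these tests are not named, and nothing restricts the analysis to patients eligible for an implant.

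The eligibility rule appears twice. Introduction and Background: "Patients keep voiding diaries during the test stimulation, and if they demonstrate a 50% or greater improvement in symptoms they are eligible for implantation". Methods and Procedures: "if a 50% or greater improvement in symptoms (number of voids, number of incontinent episodes, or less urgency) is documented they will be eligible". The item collected is a single figure: "Percent improvement in symptoms as determined by pre and post PNE voiding diaries" (Data Collection). It is not tied to any one of the three qualifying measures.

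On timing: "Patients will be randomized just before PNE by block randomization" (Methods and Procedures). On size: "We plan to enroll approximately 200 patients in the study" (same section) and "Most studies report a 40% to 50% implantation rate following PNE" (Introduction and Background).

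**The concern.** The factor under test and the gate to the outcome come from the same diaries. A patient below 50% improvement is not eligible; a patient at or above it is. If implanted and non-implanted patients are then compared on percent improvement, a large difference is built in before any data are collected.

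Percent improvement is also not a baseline characteristic. It is a response observed after randomisation and after PNE, listed beside age, race and previous treatments. The demographic label changes no result by itself. The risk is that a very small p-value in that table is read as a discovered predictor when it mainly shows that the protocol was followed. If the recorded percentage matches the qualifying measure poorly, the result is weaker but harder to interpret.

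**Working it through.** The plan gives no figure for this analysis, so there is none to reproduce. The question is how large an association the rule alone would create.

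**Inputs from the protocol.** N = 200; implantation 40-50%; eligibility at 50% improvement or more; unpaired t-test.

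**Assumed inputs.** No arm effect; 40-70% of patients meet the rule (r); 70-100% of those are implanted (u); SD of percent improvement 20, 30 or 40 points. Seven r/u settings with implantation i = r × u between 40% and 50% were used: 40/100, 50/80, 50/90, 50/100, 60/70, 60/80 and 70/70. The comparison is implanted v not implanted, inferred from the stated aim.

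**Step 1: recorded percentage is the qualifying percentage.** Values were normal, capped at 100, with no implants among ineligible patients; 7 settings × 3 SDs × 1,000 trials = 21,000.
- p < 0.05 in 21,000 of 21,000 (largest p 5e-6).
- Median t 8.1 (70/70, SD 20) to 20.4 (50/100, SD 40).
- Mean difference 19 points (70/70, SD 20) to 61 points (40/100, SD 40).
- Median AUC 0.80 (70/70) to 1.00 (full uptake).

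*Hand check at 70/70, uncapped normal.* In SD units, the eligible mean lies φ(z)/r = 0.3477/0.70 = 0.497 above the overall mean. Implanted patients share that mean, so the implanted minus non-implanted difference is 0.497/(1 − i) = 0.497/0.51 = 0.974 SD, or 19.5 points at SD 20. The within-group SD is √(1 − 0.49 × 0.51 × 0.974²) = 0.873. The standard error is 0.873 × √(1/98 + 1/102) = 0.1236, so t ≈ 0.974/0.1236 = 7.9. The AUC is [(1 − r) + ½(r − i)]/(1 − i) = (0.30 + 0.105)/0.51 = 0.79. Both agree with the simulation.

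**Step 2: recorded percentage only correlates with the qualifying one.** Uncapped normal, all seven settings, 0 or 5% implants among ineligible patients (5% lifts implantation to 42.5-52.5%), 10,000 trials each.

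| Correlation | Trials with p < 0.05, all settings | At 70/70 (0% / 5% ineligible implanted) |
|---|---|---|
| 0.7 | 99.7-100% | not listed separately |
| 0.5 | 89.9-100% | 93.9% / 89.9% |
| 0.3 | 48.6-93.6% | 54.7% / 48.6% |
| 0 | 4.4-5.5% | not listed separately |

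*Hand check at 70/70, correlation 0.3.* The difference is 0.3 × 0.974 = 0.292 SD, the standard error 0.140 and t ≈ 2.09. The chance of exceeding 1.972 is Φ(0.12) ≈ 55%, as simulated.

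**Step 3: eligible patients only.** With uptake independent of the size of improvement, the five settings with uptake below 100%, SD 20-40, capped and uncapped, 10,000 trials each: 4.5-5.2% significant. Once the rule is conditioned out, the association disappears.

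A separate simulation with other assumptions (SD 25, 45-65% eligible, 70-100% uptake, 0-10% implants among ineligible patients) gave the same picture: 100% significant in the full sample, mean differences of about 22 to 41 points, and about 4-6% among eligible patients.

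**The case against.** The case against is mainly about weight.

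- **The analysis is not strictly circular.** An eligible patient may decline; Potential Risks treats going on to the implant as the patient's decision. This stands, but at 70% response with 70% uptake, the setting where declining weakens the link most, every Step 1 trial was still significant.
- **The rule can be met on any of three measures, and the recorded percentage may be a different one.** This also stands, and it makes the true size unknown: roughly 5% to 100% of trials significant, depending on the correlation. A correlation near zero between two summaries of the same diaries is implausible. The ambiguity is a further reason to define the variable.
- **The groups for the t-test are inferred.** True. The sentence could also cover randomised groups, but for a list of factors associated with implantation, implanted v not implanted is the natural reading.
- **The eligible-only 5% is true by construction, because uptake was assumed unrelated to size of improvement.** Correct. Step 3 shows that the rule is sufficient to create the association, not that it would be the only source in this trial.
- **A test among eligible patients would be valid and would ask a real question.** Also correct. It would rest on few decliners, however: 200 × 0.70 × 0.30 = 42 at 70/70, 200 × 0.50 × 0.10 = 10 at 50/90, and none at full uptake. Description is the safer default.
- **It is one of four listed factors, no multivariable model is planned, and the rule is stated openly.** All true. This limits the damage to one secondary result, but finding such factors is the only stated secondary aim.

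**Conclusion.** The concern holds. Followed as written, and on the natural reading of the comparison groups, the plan yields a secondary result that largely restates its own eligibility rule. If the recorded percentage is the qualifying one, significance is practically certain whatever the arms do. At a correlation of 0.5 it is very likely, and at 0.3 about as likely as not in the weakest settings. These sizes depend on the assumed response, uptake, SD and correlation; only the sample size, the implantation range and the 50% threshold are the protocol's. The primary comparison of implantation rates is untouched, so this should be corrected before analysis but does not threaten the main conclusion.

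**What to change.** 1. Remove percent improvement from the factors tested for association with implantation, or report it descriptively among eligible patients only. Keep age, race and previous treatments.
2. Report percent improvement by randomised group as a supportive secondary outcome, as a difference with its 95% confidence interval. Randomisation supports that comparison.
3. State which diary measure or measures (voids, incontinent episodes, urgency) define the percentage for this analysis.
4. Optionally, report the proportion with at least 50% improvement by group, which helps separate response from uptake.

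The cost is a few sentences and one or two extra secondary comparisons. The variable is already collected, and enrolment, procedures and the primary outcome do not change.

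Precision would be modest. Assuming 100 per arm, the 95% half-width for the proportion is 1.96 × √(2p(1 − p)/100), that is 12.7 points at p = 0.7 and 13.9 at p = 0.5. For the mean it is 1.972 × SD × √(2/100), that is 5.6, 8.4 and 11.2 points for SD 20, 30 and 40.

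The optional responder proportion overlaps with the primary outcome. The correlation between responding and being implanted is phi = i(1 − r)/√[r(1 − r) i(1 − i)]. At 70/70 this is 0.147/√(0.21 × 0.2499) = 0.64; at 50/80 it is 0.20/√(0.25 × 0.24) = 0.82; at full uptake it is 1.00. Its value is therefore small when uptake is high.

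### The secondary aim of identifying factors associated with implantation rests on separate t-tests and chi-squared tests, which give crude association only, with no effect size and no adjustment for correlated factors

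*Combined protocol and SAP*

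**What the plan says.** Under Data Analysis and Statistical Methods the protocol sets the aim: "Secondary outcomes will identify demographic and perioperative factors associated with increased rates of implantation". It then lists the factors: "Demographic factors will include age, race, previous treatments, and percent improvement in symptoms as determined by pre and post PNE voiding diaries". The methods follow in one sentence: "Continuous variables will be compared using the non-paired T-test and categorical variables will be compared using the chi-squared test".

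That sentence does not say whether it serves the comparison of arms, the comparison of implanted with non-implanted women, or both. No other method is given for the secondary aim. The document contains no regression, stratification, adjustment, effect estimate or confidence interval, and it does not label the secondary results as unadjusted or exploratory.

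Two other places bear on the point. The Data Collection list includes BMI, preoperative diagnosis, previous treatments and whether the device was implanted within 3 months of PNE, so the data for an adjusted model will exist. The Introduction and Background says of the test stimulation that "if they demonstrate a 50% or greater improvement in symptoms they are eligible for implantation", which ties one of the listed factors directly to the outcome.

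**The concern.** An aim of identifying factors is usually read as saying which characteristics matter. Separate tests fall short of that in two ways.

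- **No effect on the rate.** A t-test compares, say, mean age in implanted and non-implanted women. It does not say how the chance of implantation changes with age, although the aim is worded in terms of implantation rates. A chi-squared test by itself gives a p-value, and the plan promises no difference, ratio or interval with it.
- **No separation of correlated factors.** Age, number of previous treatments, diagnosis and BMI may well be correlated. If one of them influences implantation, the others can show an association only because they accompany it.

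At stake is how the secondary results are read. Unadjusted findings without a label may be taken as factors that matter in their own right.

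**Working it through.** **Plan's own figure.** There is none to reproduce. The plan states "We plan to enroll approximately 200 patients in the study" but gives no significance level, power or effect size.

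**Inputs from the protocol.** n = 200 (Methods and Procedures). Implantation rate 40% to 50% (Introduction and Background), midpoint 45%.

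**Assumed inputs, not in the protocol.** Two-sided 5% level. Factor A affects implantation with an odds ratio (OR) of 1.5 or 2.0 per standard deviation (SD). Factor B has no effect of its own but has correlation r with A. Both are continuous.

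**Step 1: standardised difference in A between implanted and non-implanted women.** d = ln(OR) × k, where k is the mean of p(1−p) over women divided by 0.45 × 0.55.
- OR 1.5: 0.405 × 0.962 = 0.390
- OR 2.0: 0.693 × 0.903 = 0.626

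**Step 2: expected t-statistic for B.** δ = r × d × √(200 × 0.45 × 0.55) = r × d × √49.5 = r × d × 7.04.

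**Step 3: chance that B is significant.** P(Z > 1.96 − δ) + P(Z < −1.96 − δ).

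| r | δ, OR 1.5 | B significant | δ, OR 2.0 | B significant |
|---|---|---|---|---|
| 0 | 0 | 5% | 0 | 5% |
| 0.1 | 0.27 | 6% | 0.44 | 7% |
| 0.2 | 0.55 | 8% | 0.88 | 14% |
| 0.3 | 0.82 | 13% | 1.32 | 26% |
| 0.5 | 1.37 | 28% | 2.20 | 60% |

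A simulation of the t-test (20,000 trials per setting) agrees to within about one percentage point. Rates of 40% and 50% give nearly the same figures.

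**Step 4: after adjustment.** In a logistic model with A, B and arm (2,000 simulated trials per setting, rates of 40% and 50%, r from 0 to 0.7), B was significant in 4% to 7% of trials, which is about the nominal 5%.

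**Step 5: room for a model.** 200 × 0.40 = 80 and 200 × 0.50 = 100 implants. At 10 events per coefficient (a rule of thumb, assumed) that allows about 8 to 10 coefficients. Arm, age, BMI and number of previous treatments use 4. Race in two or three groups adds 1 or 2, and diagnosis in three or four groups adds 2 or 3. The total is 7 to 9. The groupings would have to be chosen to stay at 8 if the rate is 40%.

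**Step 6: percent improvement.** The other named factors are known before PNE. Percent improvement is calculated from diaries kept before and after PNE, and 50% or more is the eligibility rule. It is close to the outcome itself and may lie on the path from a baseline factor to implantation. Adjusting for it could hide the association that the aim is looking for.

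**The case against.** The strongest reply is that the protocol speaks only of association. It does not claim predictors or independent effects, and a one-factor test answers a question about crude association correctly. In the calculation above, B really is associated with implantation, through A, so a significant test is not an error in that sense. This stands. It means the plan is incomplete for its purpose, not that its tests are invalid.

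The size also rests on assumptions. At correlations of 0.1 or below the excess is negligible, and the calculation uses two continuous factors while race is categorical and previous treatments may be. This stands too, and it is why the range is shown.

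A reader might infer more than the documents support:

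- **That testing several factors is what condemns the plan, and a model cures it.** It does not. One model with six null covariates each tested at 5% still gives at least one false positive in about 27% of trials (1 − 0.95^6 = 26.5% if independent). The exploratory label deals with this, not the model.
- **That previous treatments would go into one table with overlapping cells.** The collected item is "Previous treatments for urinary urgency, frequency, retention, and/or urinary or fecal incontinence". The plan does not say how it will be coded, and a yes/no table per treatment would fit the text.
- **That leaving out arm biases the factor results.** The protocol says "Patients will be randomized just before PNE by block randomization to either Group 1 or Group 2", so arm cannot systematically confound baseline factors. Including it is good practice but not the correction of an error.
- **That BMI and diagnosis are wrongly left out.** Collecting a variable does not oblige the plan to test it.

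**Conclusion.** The point holds as a cheap improvement to a secondary analysis. The stated tests describe crude association, give no effect size for the implantation rate, and cannot distinguish a factor that matters from one correlated with it. With 200 women, 45% implanted and a true odds ratio of 1.5 to 2.0 per SD, the consequence ranges from almost nothing at correlation 0.1 to a majority of trials at correlation 0.5 with the larger odds ratio. The true correlations and effects are unknown, so the list of factors may include confounded ones. The documents do not support saying that it will. The randomised comparison of implantation rates between arms does not depend on this.

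**What to change.** For the secondary aim only, add a paragraph along these lines:

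> Factors associated with implantation within 3 months of PNE will be examined in one pre-specified logistic regression on randomised arm, age, BMI, race (sparse categories combined), grouped preoperative diagnosis and number of previous treatments, limited to about 8 to 10 coefficients according to the number of implants. Odds ratios with 95% confidence intervals will be reported. The analysis is exploratory. One-factor t-tests and chi-squared tests will be presented as unadjusted and descriptive. Percent improvement will be reported separately and not entered in the model, because it is measured after PNE and a 50% improvement is the eligibility rule for implantation.

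The groupings of race and diagnosis should be fixed before the outcome data are examined. If the investigators prefer to keep only the one-factor tests, the minimum is to label them unadjusted and exploratory and to report implantation rates or odds ratios with intervals.

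The cost is one paragraph. Every baseline variable in the model is already on the Data Collection list. The downside is somewhat wider intervals for each factor and fewer nominally significant factors.

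### The primary comparison is implicitly an unadjusted chi-squared test with no stated confidence interval; pre-specified adjustment for baseline data already collected would give a modest, conditional gain in precision

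*Combined protocol and SAP*

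**What the plan says.** Under Data Analysis and Statistical Methods, "The primary outcome will be the difference in the rate of implantation of InterStim after PNE in each group". No test is assigned to that outcome by name. The only methods given are in one general sentence, which assigns an unpaired t-test to continuous variables and adds that "categorical variables will be compared using the chi-squared test". Implantation is yes or no, recorded under Data Collection as "Whether or not InterStim implanted within 3 months of PNE", so the primary test is by implication an unadjusted chi-squared test. The protocol states no model, covariate, confidence interval, significance level, power or margin.

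Data Collection also lists age, race, BMI, "Preoperative diagnosis" and previous treatments. In the analysis section, age, race and previous treatments appear only in a secondary search for factors related to implantation. Percent improvement on the diaries is grouped with them as a demographic factor.

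Under Methods and Procedures, "We plan to enroll approximately 200 patients in the study", and "Patients will be randomized just before PNE by block randomization to either Group 1 or Group 2". No stratification factor or allocation ratio is given. The background states: "Most studies report a 40% to 50% implantation rate following PNE (1".

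**The concern.** The hypothesis is that fluoroscopy makes no significant difference to conversion. A non-significant chi-squared test does not show that. What the trial can support depends on which differences it rules out, and so on the confidence interval for the difference in rates. The plan provides no interval.

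It also ignores, in the one comparison the trial was set up to make, patient characteristics that are known before randomisation and already being extracted. If some of them predict implantation, adjusting for them narrows the interval and corrects for chance imbalance between arms. If adjustment is not specified in advance, any made after the data are seen is open to challenge. The list of factors also holds a trap: percent improvement is measured after randomisation and determines eligibility for implantation, so adjusting for it would remove part of the effect under study.

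**Working it through.** **Inputs from the protocol.** Total about 200 patients; binary outcome within 3 months of PNE; background implantation rate 40% to 50%.

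**Assumed.** 1:1 allocation (100 per arm), two-sided 95% interval, no dropout, and the prognostic strength of the covariates, on which the protocol gives nothing.

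**The plan's own figure.** The 200 cannot be reproduced, because no target difference, margin, significance level or power accompanies it.

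**Crude precision.** Half-width = 1.96 × √(2p(1−p)/100).
- p = 0.40: 1.96 × √(0.48/100) = 13.6 points
- p = 0.45: 1.96 × √(0.495/100) = 13.8 points
- p = 0.50: 1.96 × √(0.50/100) = 13.9 points

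**Effect of adjustment.** Trials were simulated with 100 per arm and about 45% implanted, and analysed by logistic regression standardised back to a risk difference. The ratio V is the crude variance divided by the adjusted variance. The equivalent sample size is 200 × V, and the adjusted half-width is 13.79/√V. Each cell gives the result with two covariates, then with six.

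| Assumed odds ratio per SD | Share of outcome variance (approx.) | V | 200 patients act like | Half-width (points) |
|---|---|---|---|---|
| 1.0 | 0 | 0.99 / 0.97 | 198 / 194 | 13.86 / 14.00 |
| 1.5 | 4% | 1.03 / 1.02 | 206 / 204 | 13.59 / 13.65 |
| 2.0 | 10% | 1.10 / 1.07 | 220 / 214 | 13.15 / 13.33 |
| 2.5 | 15% | 1.16 / 1.15 | 232 / 230 | 12.80 / 12.86 |

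Two separate simulations with three covariates gave V of 1.01 and 1.02 at an odds ratio of 1.5, 1.10 and 1.11 at 2.0, and 1.14 and 1.16 at 2.5, so simulation error is about 0.02.

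**Analytic check.** If the covariates explain a share R² of the outcome variance, V is about 1/(1−R²). For R² = 0.10 this is 1/0.90 = 1.11, or about 222 patients. The simulated values are slightly lower because estimating the coefficients has a cost.

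**Scale of reporting.** With five simulated covariates, the standard error of the log odds ratio rose on adjustment from 0.286 to 0.304, 0.319 and 0.343 as R² rose through about 0.07, 0.15 and 0.26. The narrowing therefore appears only if the result is returned to the risk-difference scale, which is also the scale of the stated primary outcome.

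**Missing covariates.** With a six-parameter model and an assumed 5% of patients dropped for a missing covariate, V was 0.91, 0.95 and 1.01 at odds ratios of 1.0, 1.5 and 2.0. Dropping patients removes the gain.

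**What adjustment cannot do.** Against an assumed 15-point non-inferiority margin, power with 100 per arm is 56–58% crude, 61–63% at R² = 0.10 and 69–71% at R² = 0.25. Against an assumed 10-point margin it is 29–30% crude and 37–39% at R² = 0.25.

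**The case against.** The case against is substantial. Under randomisation the chi-squared test is valid and the crude difference is unbiased. No stratification factor is named, so nothing in the design requires adjustment. The choice is between two valid analyses, and the gain is about half a point to one point of half-width even with a fairly strong predictor. All of that stands, and it limits the point to one of efficiency.

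Four stronger readings are tempting, and the protocol does not support them.
- A reader might infer that a planned interval is too wide. No interval is planned, so the first gap is its absence.
- A reader might infer that the protocol names predictors of implantation. It says that finding associated factors is a secondary aim, which leaves the question open. BMI and preoperative diagnosis are not among the factors it names for that search.
- A reader might infer that any baseline measure can be used without further data. A diary is kept before the procedure, but Data Collection lists only percent improvement from it, and facility is not listed. Using either would need a change to the data list.
- A reader might infer that adjustment is free of risk. With uninformative covariates about 1 to 3% of precision is lost, and more if patients with missing covariates are dropped.

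None of this defeats a short model that uses only listed variables and keeps every patient in the comparison. Standardising to a risk difference also answers the worry that adjustment changes the quantity being estimated.

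**Conclusion.** The point holds as a recommended improvement, not as an error in the plan. The implied primary analysis is valid but leaves collected baseline data unused, and it comes without an interval. With 100 per arm and about 45% implanted, adjustment would make 200 patients act like about 204 to 206, 214 to 220 or 230 to 232 at assumed odds ratios per SD of 1.5, 2.0 and 2.5, and like 194 to 198 if nothing is prognostic. These figures rest on 1:1 allocation, no dropout, complete or imputed covariates, and prognostic strengths that the protocol does not give.

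A reader might infer that adjustment would make the no-difference claim secure. It would not: the absent margin and sample-size rationale are the larger gaps, and adjustment fills neither.

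**What to change.** Amend Data Analysis and Statistical Methods, before any outcome is examined by arm, to state the following.

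- **Primary analysis:** logistic regression of implantation within 3 months of PNE on arm, age, preoperative diagnosis grouped into a few named categories, and previous treatments coded as one term. Report the standardised (marginal) risk difference with its 95% confidence interval. It is the average predicted probability over all patients with arm set to Group 1, minus the same with arm set to Group 2.
- **Missing covariates:** simple imputation, so that no randomised patient is dropped for lack of a covariate.
- **Supportive analysis:** the chi-squared test and the crude risk difference with its 95% interval.
- **Exclusions:** no adjustment for percent improvement, which is measured after randomisation. No reliance on the pre-PNE diary rate or facility, which are not listed data items.

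The cost is a few sentences, one model, and a decision on how to group diagnoses and code previous treatments. No new patients or data items are needed. The statistical cost is the 1 to 3% loss of precision if the covariates prove uninformative. The margin and the basis for the 200 patients still have to be written separately.
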